E-cigarettes present a potential innovative solution to the challenges of reducing tobacco smoking among adults with SMI. E-cigarettes provide an experience close to tobacco smoking, which may increase their acceptability and use. The long-term health consequences of e-cigarette use are unknown. However, no negative health consequences of short-term use as in the current study have been reported, and most researchers agree that e-cigarettes are likely healthier than tobacco smoking¹⁷. Importantly, two small open-label studies observed decreased tobacco smoking among non-treatment seeking adults with schizophrenia and schizoaffective disorder following one month of access to e-cigarettes^{18,19}. Such results are promising as individuals with schizophrenia exhibit severe tobacco smoking, even when compared to others populations with SMI.

In the current pilot proposal, adults with SMI (N=10/group) interested in reducing their tobacco smoking will be randomized to receive either nicotine replacement therapy (NRT; patch 21 mg) as the standard of care or NRT plus e-cigarettes (36 mg/ml) for one month according to a double-blind, randomized controlled trial design. We will use a previously evaluated e-cigarette including nicotine liquid solutions that have been independently tested.

SPECIFIC AIMS AND HYPOTHESES

Specific Aim 1: Assess feasibility, acceptability, and safety of providing e-cigarettes to adults with SMI to reduce tobacco smoking.

Hypothesis 1.a: *We predict that a high proportion of participants will consent to participate ($\geq 80\%$) and complete ($\geq 70\%$) the study.*

Hypothesis 1.b: *We predict that end of study participant satisfaction ratings will indicate high acceptability of e-cigarettes and likelihood of future use.*

Hypothesis 1.c: *We predict e-cigarettes will be safe as measured by frequency of adverse events (AEs) and side-effects. In addition, we predict e-cigarettes will not be associated with increases in symptom specific measures.*

Specific Aim 2: **To compare reductions in tobacco smoking between NRT vs NRT + e-cigarettes (36 mg/ml).**

Hypothesis 2: *Significantly greater reductions in smoking (tobacco cigarettes/day, breath CO) will be observed in the NRT + e-cigarette vs. the NRT condition.*

BACKGROUND AND RATIONALE

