E-Cigarette and Tobacco Smoking Related Assessments. Tobacco smoking will be assessed using a combination of breath CO, urinary cotinine, and self-report via time-line follow-back. Standard questionnaires will be used to assess a number of tobacco-smoking related measures. The Fagerstrom Test for Nicotine Dependence (FTND) will be used to assess tobacco cigarette dependence⁴². The Questionnaire of Smoking Urges (QSU) will be used to assess craving for tobacco cigarettes⁴³. The Minnesota Nicotine Withdrawal Questionnaire (MNWQ) will be used to assess withdrawal symptoms from tobacco cigarettes⁴⁴. The Stages of Change Questionnaire will be administered to assess desire to quit from tobacco cigarette smoking⁴⁵. The Clinical COPD Questionnaire (CCQ) will be used to assess changes in COPD-related symptoms⁴⁶. Additional smoking-related assessment will include the Confidence to Quit (CQ) and Hooked on Nicotine Checklist (HONC). E-cigarette related questionnaires developed and provided by [name] will be used to evaluate e-cigarette dependence, patterns of use, evaluation of using e-cigarettes, and side-effects. These questionnaires will include Confidence to Quit, E-Cigarette Dependence Scale, E-Cigarette Patterns of Use, E-Cig Evaluation, E-Cig Side Effects, and Hooked on Nicotine Checklist.

Assessing Changes in Symptoms Relevant to SMISchizophrenia. The Brief Psychiatric Rating Scale (BPRS)⁴⁷ will assess symptom severity among individuals with SMI. Potential changes in key cognitive domains associated with will be assessed with the MATRICS Consensus Cognitive Battery (MCCB). The Columbia Suicide Severity Rating Scale (CSSRS) will assess suicide ideation. Changes in mood symptomatology including also anhedonia and mania will be assessed with the Beck Depression Inventory (BDI), Snaith-Hamilton Pleasure Scale (SHAPS), and the Altman Self-Rating Mania Scale (ASRM) respectively. Changes in PTSD symptoms will be assessed using the PTSD Checklist for DSM 5.

Safety and Health-Related Measures. Adverse events (AEs) and severe AEs, along with concomitant medications, will be assessed at weekly study visits. Heart Rate (HR) and blood pressure (BP) will also be assessed using standard hospital-grade equipment.

Table 1. Outline of Study Procedures and Assessments.

Procedure and Assessments	Study Visits	Week 0	Week 1	Week 2	Week 3	Week 4	Week 5
Baseline Screening		X					
Receive E-Cigarettes (36 mg/ml) and NRT Patch (21 mg)				X	X	X	X
Smoking Related Assessments							

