Breath CO, QSU, MNWQ, , TLFB, CCQ, CQ, HONC		X	X	X	X	X	X
Urinary Cotinine		X					X
FTND, Stages of Change		X					X
E-Cigarette Questionnaires				X	X	X	X
AEs, Concomitant Meds, HR, BP		X	X	X	X	X	X
BPRS, CSSRS, BDI, SHAPS, ASRM, PTSD		X	X	X	X	X	X
MCCB		X					X

DATA ANALYSIS PLAN

Preliminary data analyses will inspect baseline, group differences as well as correlations between baseline variables and specified outcomes. Baseline or demographic variables demonstrating a correlation with both predictors and outcomes, meet criteria for being potential confounders,^{i,ii} and will result in two sets of analyses: one in which the relevant variable is included as a covariate and one in which it is not. This will determine the degree to which any group differences might confound conclusions regarding treatment. Statistical analyses will use R v. 3.3.0ⁱⁱⁱ and SAS v.9.3.^{iv}

Analyses will primarily use generalized linear modeling. Continuous, count, dichotomous and time-to-event data will utilize linear, Poisson, logistic, and proportional hazards regression respectively (Proc GENMOD and PROC PHREG; SAS v. 9.3, function glm(); R v. 3.3.0). Longitudinal analyses will employ generalized linear mixed models (Proc MIXED, Proc GLIMMIX and Proc MCMC; SAS 9.3). Evaluation of distributional assumptions will use residual plots and, where possible, formal statistical tests. Depending upon statistical technique, transformations, robust estimators, stratification and/or scaling coefficients will address violations of assumptions. Analyses of cross-sectional data with missing values will utilize multiple imputation (Proc MI; SAS v.9.3)^v. Multiple imputation and maximum likelihood are robust to data missing at random. Sensitivity analyses will permit evaluation of the robustness of findings to missing data assumptions.

Specific Aim 1: Assess feasibility, acceptability, and safety of providing e-cigarettes to adults with SMI to reduce tobacco smoking.

Hypothesis 1.a: We predict that a high proportion of participants will consent to participant (80%) and complete the study (70%) completion rate. Descriptive statistics will evaluate consent and completion rates.

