Hypothesis 1.b: We predict that end of study participant satisfaction ratings will indicate high acceptability of e-cigarettes and nicotine patch and likelihood of future use. Generalized linear models will evaluate the relationships between participant satisfaction, acceptability of e-cigarettes and nicotine patch, and likelihood of future use.

Hypothesis 1.c: We predict e-cigarettes will be safe as measured by frequency of adverse events (AEs) and side-effects, and not associated with increases in negative symptoms (BPRS) or decreases in cognitive performance (MATRICS). Generalized linear modeling will evaluate relationships between adverse events/side-effects, negative symptoms, and cognitive performance.

Specific Aim 2: To compare reductions in tobacco smoking between NRT vs NRT + e-cigarettes (36 mg/ml).

Hypothesis 2: *Significantly greater reductions in smoking (tobacco cigarettes/day, breath CO) will be observed in the NRT + e-cigarette vs. the NRT condition. Generalized linear modeling will evaluate group differences in smoking reduction between NRT and NRT + e-cigarettes over time as measured by breath CO (using a Gaussian distribution) and tobacco-cigarettes/day (using a Poisson distribution).*

Power/Sample Size Considerations. For the current proposal, power will focus on Aim 2. Effect size is derived using G*Power 3.1.9.2. Assuming alpha = 0.05 and a correlation among repeated measures of 0.5, a sample size of n = 20 (n = 10 NRT and 10 NRT + e-cigarette) provides 80% power to detect a Cohen's f = 0.51 for group differences between NRT and NRT + e-cigarette. The Frequentist findings will be augmented with a Bayesian approach to characterize the probability that effect sizes of varying magnitude exist.

JUSTIFICATION

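### Hypothesis 1.b predicts a high level of acceptability, but its only stated analysis models associations between the ratings, which say essentially nothing about level

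*Combined protocol and SAP*

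**What the plan says.** Under Specific Aims and Hypotheses, Hypothesis 1.b predicts that "end of study participant satisfaction ratings will indicate high acceptability of e-cigarettes and likelihood of future use". The Data Analysis Plan restates it with the patch added: "We predict that end of study participant satisfaction ratings will indicate high acceptability of e-cigarettes and nicotine patch and likelihood of future use". Neither version says what value would count as high.

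The analysis follows in one sentence: "Generalized linear models will evaluate the relationships between participant satisfaction, acceptability of e-cigarettes and nicotine patch, and likelihood of future use".

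Hypothesis 1.a, in the same aim, is handled differently. It has numerical targets ("We predict that a high proportion of participants will consent to participant (80%) and complete the study (70%) completion rate") and a matching analysis: "Descriptive statistics will evaluate consent and completion rates". The general methods say "Analyses will primarily use generalized linear modeling" and add nothing on summarising ratings.

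On instruments, the assessments section lists for e-cigarettes: "These questionnaires will include Confidence to Quit, E-Cigarette Dependence Scale, E-Cigarette Patterns of Use, E-Cig Evaluation, E-Cig Side Effects, and Hooked on Nicotine Checklist". It gives no response scale, scoring or cut-off, and names no measure of patch acceptability or of general satisfaction. Table 1 schedules the e-cigarette questionnaires at Weeks 2 to 5.

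**The concern.** The hypothesis is about where the ratings lie on their scale. The analysis is about whether people who give a higher rating on one item also give a higher rating on another. The second question can be answered fully while the first stays open: ten participants who mostly dislike the device and ten who mostly like it can produce the same slope, correlation and p-value.

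Acceptability is one of the three components of Aim 1, and the results are meant to support a larger grant application. If the plan is followed as written, the acceptability statement in that application will rest either on models that do not address it or on a summary, and a meaning of high, chosen after the data are seen.

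**Working it through.** **Is there a figure to reproduce?** No. The plan gives no threshold, alpha or power for 1.b. Alpha of 0.05 appears only in the power statement, which is confined to Aim 2.

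**Inputs from the documents.** Ten participants per arm ("a sample size of n = 20 (n = 10 NRT and 10 NRT + e-cigarette) provides 80% power"), so at most 10 people can rate the e-cigarette and at most 20 can rate the patch, which both arms receive.

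**Inputs assumed.** Rating scale, SD, correlation between ratings, and a two-sided 0.05 test. The documents give none of these for 1.b.

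**Step 1: the algebra.** For ratings x and y, the slope is Σ(x − x̄)(y − ȳ) / Σ(x − x̄)². Replacing x by x + c and y by y + c leaves every deviation from the mean, and so the slope, correlation and p-value, unchanged. Only the intercept moves. Numerical check with n = 10: raising both ratings by 70 points left the slope at 0.861, the correlation at 0.966 and the p-value at 5.3 × 10⁻⁶.

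**Step 2: simulation on a bounded scale.** Real scales have ends, so the shift argument is only approximate there. Pairs of ratings were drawn from a bivariate normal distribution with SD 1, rounded and truncated to 1-7, n = 10. The means are those before rounding and truncation. Percentage of simulated trials with a positive correlation and p < 0.05:

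| Correlation | Low ratings (mean 2.5) | High ratings (mean 6.5) |
|---|---|---|
| 0.3 | 11% | 12% |
| 0.7 | 56% | 48% |
| 0.8 | 74% | 65% |

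Each row compares low with high at the same correlation. The differences are −1, 8 and 9 percentage points. Going down a column changes the result by more than 50 points. The outcome is driven by how strongly the ratings correlate, not by whether they are high.

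The differences at 0.7 and 0.8 come from crowding at the end of the scale, and the bottom behaves like the top: mean 1.5 gives 48% at 0.7 and 65% at 0.8.

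**Step 3: a second assumed scale.** On 0-100 with SD 5 and n = 10, mean 20 against mean 90 gives 33.4% against 32.6% at correlation 0.5, and 87.9% against 87.2% at 0.8. These agree within simulation error.

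**Step 4: precision of a direct estimate.** Exact (Clopper-Pearson) 95% intervals for the proportion favourable among e-cigarette users:

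| Favourable | 95% interval |
|---|---|
| 7/10 | 34.8% to 93.3% |
| 8/10 | 44.4% to 97.5% |
| 9/10 | 55.5% to 99.7% |
| 10/10 | 69.2% to 100% |
| 7/7 (if 70% of 10 complete) | 59.0% to 100% |

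**The case against.** The strongest reply is that the plan sets no decision rule for 1.b. It does not say that a significant slope would confirm the hypothesis, and the investigators would probably report means in any case. A fitted model also has an intercept and fitted means from which level could be read. This stands in part. The plan cannot be charged with a false success rule, because it has no rule. It remains true that it commits to no estimate of level.

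Two stronger readings are tempting, and the documents do not support either.

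- A reader might infer that 1.b can succeed with uniformly low ratings and fail with uniformly high ones. The plan defines neither outcome. Taken literally, identical ratings have no variance, so no association can be estimated whether they are all low or all high.
- A reader might infer that the analysis works against a well-liked device, because ratings near the top lose spread. Ratings near the bottom lose it equally. A contrast such as 74% for low ratings against about 12% for high ones arises only if the correlation is changed from 0.8 to 0.3 at the same time.

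It is also fair that scale, SD and correlations are assumed. The simulation illustrates a logical point and is not evidence about this trial's questionnaires. Finally, with 10 raters a binding pass mark would add little; an estimate with its interval does most of the work.

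**Conclusion.** The concern holds as a mismatch between hypothesis and analysis. Hypothesis 1.b asserts a level, its single analysis sentence addresses associations, and no other part of the document supplies an estimate of level. The Bayesian supplement concerns effect sizes and does not fill the gap.

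The invariance to a common shift needs no assumption about the data beyond ratings that vary. The simulated percentages rest on the assumed scales, SDs and correlations, and show only that low and high ratings give similar results at a given correlation.

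The consequence is moderate. This is a 20-person pilot and the ratings are descriptive, but acceptability is a named part of the first aim. The plan should be changed; the trial's conduct is not in question.

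A related gap is that the two statements of 1.b differ on whether the patch is included, and no instrument for patch acceptability is named.

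**What to change.** Replace the 1.b analysis sentence with estimation of level at the end-of-study visit (Week 5):

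- For satisfaction, acceptability and likelihood of future use, report the mean or median with a 95% confidence interval, and the number and percentage giving a favourable rating with an exact 95% interval.
- Name the questionnaire and items. Define the favourable category from the questionnaire's own response scale before the data are seen. A generic cut such as the midpoint would be arbitrary, since the documents do not describe the scale.
- Report e-cigarette ratings in the NRT + e-cigarette arm.
- Reconcile the two statements of 1.b on the patch. If it is kept, name the instrument and report patch ratings by arm, in both arms.
- State in advance what will be called high, as 1.a does for its rates, as a descriptive benchmark and not a test.
- Keep the models relating the ratings to one another as exploratory.

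For the e-cigarette this is a wording change on questionnaires already scheduled. For the patch it may need an added item, because none is named. The downside is that the acceptability claim becomes visibly imprecise, as the interval for 7 of 10 shows.

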Rates of tobacco smoking are 2-4 times higher among individuals with SMI compared to those without mental illness and the rate of smoking decreases has lagged behind that of the general population^{1,2}. Tobacco smokers with SMI are more dependent on nicotine and less likely to quit compared to those without mental illness³⁻⁵. Tobacco-smoking related death and morbidity are high among individuals with SMI, with half the deaths in this population due to tobacco related cancers, respiratory diseases, and cardiovascular conditions^{6,7}. Predominate theories point to a number of potential causal mechanisms including but not limited to: 1) alleviation from negative symptoms and cognitive deficits associated; 2) genetic, environmental, and neural deficits that increase vulnerability to tobacco dependence; and 3) increased susceptibility to withdrawal symptoms^{13,14}. Although tobacco smoking cessation is an ideal goal, many individuals with SMI are not motivated to quit tobacco smoking in the near future. As an alternative strategy, reducing tobacco smoking may result in more viable health gains. For example, smoking reduction has health benefits on its own and also increases the likelihood that smokers may initiate and succeed in quitting smoking in the future^{15,16}. However, reducing tobacco smoking also poses a number of challenges. Simply reducing the number of daily cigarettes smoked may have unintended consequences including compensatory increases in smoking and worsening of psychiatric symptoms. Additionally, two of the first-line medications for nicotine dependence (i.e., varenicline, bupropion) carry black-box warnings for increased risk of psychiatric symptoms and suicidal ideation in patients with a history of psychiatric illness.

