Study Design and Overview. We will utilize a double-blind, randomized controlled design to assess the feasibility and acceptability of using e-cigarettes to reduce tobacco smoking among individuals with SMI (schizophrenia and schizoaffective disorder, bipolar disorder, or PTSD). Participants will consist of tobacco smokers with SMI interested in reducing or quitting their tobacco smoking. Note that these two experimental conditions were chosen based on available funds and likelihood of obtaining preliminary data that would be useful in a future NIH grant application. We plan to assess other conditions in the future (e.g., placebo e-cigarette, etc.). Following a one-week baseline lead-in period, participants will be randomized to either the NRT or NRT + e-cigarette condition. Study visits will be scheduled for once a week (5 weeks total).

[figure not shown]

Figure 1. Overview of study design.

Study Procedures and Assessments

Participant Recruitment and Selection. Participants will be recruited from the ICNTP, PIRL-M, and STARS clinic. Eligible participants will meet the following inclusion criteria: 1) be diagnosed with schizophrenia or schizoaffective disorder, bipolar disorder, or PTSD and in stable medical condition (DSM-5); 2) report smoking ≥ 10 tobacco cigarettes/day and present a breath CO ≥ 10 ppm; 3) report wanting to quit or reduce their cigarette smoking; 4) be fluent in English; 5) be between 18 and 65 years of age; and 6) have a stable living situation. Participants will be ineligible if they meet the following exclusion criteria: 1) be currently pregnant or breastfeeding; 2) report wanting to quit smoking in the immediate future; 3) test positive for illicit drugs except THC; and 4) have any illness, medical condition, or use of medications, which in the opinion of the study physicians (Drs. [name] and [name]) would preclude safe and/or successful completion of the study.

Following informed consent, participants will complete an initial general evaluation protocol (HSC-MS-05-0322; General evaluation of Eligibility for Substance Abuse/Dependence Research) to assess their psychiatric status, medical evaluation, and drug use history.

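### Hypothesis 1.c gives psychiatric drug changes no role in the analysis, so its symptom scores can understate harm within an arm

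*Combined protocol and SAP*

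**What the plan says.** - **Safety criteria.** In the Data Analysis Plan, Hypothesis 1.c rests on how often adverse events and side-effects occur, and on e-cigarettes being "not associated with increases in negative symptoms (BPRS) or decreases in cognitive performance (MATRICS"). The Specific Aims section words the symptom part more broadly, without naming scales.
- **Model.** Generalized linear modeling is to relate adverse events, negative symptoms and cognition to one another. Neither treatment arm nor medication change is named as a term.
- **Medication data.** Under Safety and Health-Related Measures, adverse events, "along with concomitant medications, will be assessed at weekly study visits". Table 1 marks them at Weeks 0 to 5.
- **Score schedule.** Table 1 has BPRS and the other symptom scales at every visit, but the MCCB (the MATRICS battery) only at Weeks 0 and 5. Hypothesis 1.c fixes no BPRS time point.
- **Entry.** Participants must be "in stable medical condition (DSM-5"), and the study physicians may exclude on medication use. The supplied text has no rule on medication after entry.
- **Other analysis rules.** The covariate rule covers baseline and demographic variables only. The sensitivity analyses cover missing-data assumptions only.

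**The concern.** The protocol's opening summary warns that simply cutting down cigarettes may have "unintended consequences including compensatory increases in smoking and worsening of psychiatric symptoms". Participants have schizophrenia or schizoaffective disorder, bipolar disorder or PTSD, so someone who worsens may have psychiatric medication started or increased during the study month. A score taken after such a change reflects product and drug together. It is not missing, so the missing-data analyses do not reach it. It is not a baseline variable, so the covariate rule does not reach it either. It enters the analysis as if nothing had happened.

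This matters because a null result is the favourable result for Hypothesis 1.c. Anything that shrinks a real worsening helps to confirm it, and the Justification section says the results will serve as preliminary data for the next grant application.

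**Working it through.** **1. The plan's only power figure.** The section on power states: "For the current proposal, power will focus on Aim 2". The inputs are alpha 0.05, correlation 0.5, N = 20 and f = 0.51, for 80% power. The number of measures m is not stated. For the between-groups F test with 1 and 18 df, λ = f²·N·m / (1 + (m−1)ρ):
- m = 5: λ = 0.2601 × 100 / 3 = 8.67, power 79.5%
- m = 6: λ = 0.2601 × 120 / 3.5 = 8.92, power 80.6%

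The stated figure reproduces with five or six measures. It says nothing about Hypothesis 1.c, which has no power, margin or threshold.

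**2. A score taken once at the end (MCCB, or BPRS at the last visit).** Let a share w of an arm worsen by δ, and let a share t of those be back at baseline when scored. The observed arm shift is w × δ × (1 − t). Assume w = 0.3 and δ = 1.5 SD (not in the documents):
- none treated back: 0.3 × 1.5 = 0.45 SD
- one of three: 0.45 × 2/3 = 0.30 SD
- two of three: 0.45 × 1/3 = 0.15 SD
- all three: 0 SD

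For the MCCB this also assumes that a drug change would restore cognition, which the documents do not say.

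**3. A weekly score averaged over visits (BPRS in a mixed model).** Assume 2 of 10 worsen by 2 SD over four post-baseline visits:
- untreated: 0.2 × 2 = 0.40 SD
- back at baseline after two visits: 0.40 × 2/4 = 0.20 SD; last visit 0
- back at baseline after one visit: 0.40 × 1/4 = 0.10 SD; last visit 0

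With 1 to 5 of 10 worsening by 1 to 2 SD, the untreated shift runs from 0.1 to 1.0 SD. Masking at two of four visits halves it to 0.05 to 0.5 SD.

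**4. Chance of detection.** With 10 per arm, four visits and correlation 0.5, SE = √((1 + 3 × 0.5)/4) × √(2/10) = 0.791 × 0.447 = 0.354. Approximate power is Φ(shift/SE − 1.96):
- 0.40 SD: Φ(1.13 − 1.96) = 20%
- 0.20 SD: Φ(0.57 − 1.96) = 8%

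**5. Direction between arms.** Suppose both arms truly shift by 0.45 SD as in step 2, so the true difference is 0. If two cases are treated back in the NRT arm only, the observed difference is 0.45 − 0.15 = +0.30 SD, against e-cigarettes. If the two are in the e-cigarette arm, it is −0.30 SD. The sign depends on where the treated cases fall.

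**6. What a count would show.** In step 2, a count of participants who worsened or had psychiatric medication added or increased stays at 3 of 10 whatever t is. Its exact 95% interval is about 7% to 65%. For 0 of 10 the upper limit is 1 − 0.025^(1/10) = 31%.

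**The case against.** A reader might infer that a participant who worsens and is treated is simply recorded as unharmed. The documents do not support that. Adverse events and side-effects are themselves a criterion of Hypothesis 1.c and are assessed at the same visits, so treated worsening can be counted there. BPRS is also weekly, and longitudinal data go to mixed models, so a rise at or before the visit of the drug change stays in the data. What remains is that nothing in the text requires a psychiatric drug change to be reported as an adverse event, and event counts do not correct the scores.

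A reader might also infer that the error always favours e-cigarettes. Within an arm, successful treatment pulls the score change toward no harm. Between arms the direction is open: both arms receive the patch and both aim to cut down, and the protocol's warning concerns cutting down, not e-cigarettes. There is no placebo device, so medication decisions could differ by arm, but the documents do not say in which direction.

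Two further objections are fair. Analysing scores regardless of medication change is a legitimate target, and it should stay. And with about 20% power for an undiluted 0.4 SD shift, the scores would often miss harm anyway. That second point supports a participant-level count beside the arm means, and caution in reading a null.

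**Conclusion.** The point holds in limited form. The medication log is collected at every visit and used in no stated analysis, so the within-arm symptom change in Hypothesis 1.c can understate harm. The MCCB and any last-visit BPRS comparison are most exposed; visit-averaged BPRS is diluted, not erased. The documents give no rate of worsening, size of worsening or rate of drug change, so the SD figures above are illustrations and not estimates of bias. The net effect on an arm comparison cannot be signed, and the model sentence for 1.c does not name that comparison. This is an inexpensive improvement to a pilot's safety reporting, and it bears on what a null symptom result may be said to show. It does not touch the Aim 2 analysis or the sample size.

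**What to change.** Keep the score analysis as planned and add the following to Hypothesis 1.c:

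- **Count by arm, with exact 95% confidence intervals:** participants with either symptom worsening beyond a threshold, or a new or increased psychiatric medication, after product start. Before analysis, fix the threshold, the scale it applies to, which drugs count as psychiatric, and the date that defines product start.
- **BPRS sensitivity analysis:** after a medication change, use the worse of the observed score and the worst score recorded up to the change. This never lowers a recorded score. Plain replacement by the earlier worst value could, if the participant is still worse at the next visit.
- **MCCB:** do not impute. The only earlier value is Week 0, so carrying it forward would set the change to zero. Flag the affected participants.
- **Wording:** base any statement that symptoms did not increase on both the scores and the count.

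The cost is a few sentences in the plan, one table and one sensitivity analysis, all from data already collected, with no added visits or participants. The downside is that unrelated medication changes add noise, and with 10 per arm the intervals will be wide.

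### The stated analysis for the safety hypothesis (1.c) relates outcomes to one another and names no arm comparison, so as written it estimates no e-cigarette effect

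*Combined protocol and SAP*

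**What the plan says.** The Data Analysis Plan states Hypothesis 1.c as a claim about exposure: e-cigarettes will be safe, judged by how often AEs and side-effects occur, and "not associated with increases in negative symptoms (BPRS) or decreases in cognitive performance (MATRICS"). The analysis sentence that follows is: "Generalized linear modeling will evaluate relationships between adverse events/side-effects, negative symptoms, and cognitive performance". It is the only analysis given for 1.c.

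The analysis for Hypothesis 2, a few lines below, is written differently: "Generalized linear modeling will evaluate group differences in smoking reduction between NRT and NRT + e-cigarettes over time". Arm and time are both there.

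The general text at the start of the Data Analysis Plan names model families and software, including "Longitudinal analyses will employ generalized linear mixed models". It mentions treatment only when discussing baseline covariates, where two sets of analyses are meant to show how far "any group differences might confound conclusions regarding treatment".

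In Specific Aims and Hypotheses, 1.c is broader: "we predict e-cigarettes will not be associated with increases in symptom specific measures". Table 1 schedules "BPRS, CSSRS, BDI, SHAPS, ASRM, PTSD" and "AEs, Concomitant Meds, HR, BP" at every visit from Week 0 to Week 5, and the MCCB at Weeks 0 and 5.

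**The concern.** The hypothesis asks what e-cigarettes do. The model asks whether participants with more AEs also have worse symptoms or cognition. These are different questions, and the second can be answered without knowing who received an e-cigarette.

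Safety is one of the three components of Aim 1, and the pilot is meant to support a larger trial. If the sentence is followed literally, a significant result could reflect nothing more than AEs and symptoms going together in the same people. A null result could sit alongside real worsening in the e-cigarette arm. Either could be carried into the next application as evidence on safety when it is not.

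Hypothesis 1.b has a milder form of the same problem. Its model relates satisfaction, acceptability and likelihood of future use to one another, but the prediction is that the ratings are high. An association between ratings says nothing about their level.

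**Working it through.** **1. The two analysis sentences side by side.**

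| | Hypothesis 1.c | Hypothesis 2 |
|---|---|---|
| Claim | E-cigarettes are safe and do not worsen symptoms or cognition | Larger smoking reduction with NRT + e-cigarettes |
| Variables in the analysis | AEs/side-effects, negative symptoms, cognition | Breath CO, cigarettes/day |
| Arm named | No | Yes |
| Time named | No | Yes |

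**2. The plan's own figure.** The only power statement is for Aim 2: 80% power for f = 0.51 with N = 20, alpha 0.05 and repeated-measures correlation 0.5. The number of measures m is not stated. For a between-group repeated-measures test, λ = f²·N·m/(1 + (m − 1)·0.5), with 1 and 18 df.
- m = 5: λ = 0.2601 × 100/3 = 8.67, power 79.5%.
- m = 6: λ = 0.2601 × 120/3.5 = 8.92, power 80.6%.

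The figure reproduces. It is an arm comparison and does not cover 1.c.

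**3. How the stated 1.c model behaves.** Assumptions, none taken from the documents except the 10 per arm and alpha 0.05 (taken as two-sided): one normal symptom change score with SD 1, one normal AE-burden score, and within-arm correlation ρ between them. The test is the slope t-test with 18 df, and each setting has 100,000 simulated trials. With no e-cigarette effect on anything, the model is significant in:

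| ρ | Significant |
|---|---|
| 0 | 5% |
| 0.3 | about 25% |
| 0.5 | 64% |

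So the result is driven by ρ. Now let e-cigarettes raise both symptoms and AEs by 1 SD at ρ = 0.3: the model is significant in 53% of trials, fewer than the 64% with no harm at ρ = 0.5. A reader who sees the result cannot tell these situations apart.

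**4. How an arm contrast behaves.** Two-sample t-test, 10 per arm, noncentral F with λ = d²·10/2 and 1 and 18 df:

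| Harm d (SD) | 0 | 0.5 | 1 | 1.5 |
|---|---|---|---|---|
| Significant | 5% | 19% | 56% | 89% |

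This responds to harm and holds its 5% level when there is none.

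**5. Precision after the change.**
- Week 5 difference, unadjusted: 2.101 × √(2/10) = 0.94 SD.
- Adjusted for baseline at correlation 0.5, so residual variance is 1 − 0.25 = 0.75: 2.110 × √(0.75 × 2/10) = 0.82 SD.
- The same with 7 completers per arm, the plan's predicted 70%: 2.201 × √(0.75 × 2/7) = 1.02 SD.
- No events in 10 participants, exact two-sided 95% upper limit: 1 − 0.025^(1/10) = 31%.

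**6. Hypothesis 1.b.** In a linear model, subtracting the same constant from every rating leaves each slope and p-value unchanged, so the model cannot separate high ratings from low ones. If all 10 e-cigarette participants gave the top rating, no slope could be estimated. The level would be 10/10, with exact 95% CI from 0.025^(1/10) = 69% to 100%.

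**The case against.** The strongest reply is that the sentence is shorthand. The sentence before it is about e-cigarettes, the trial has only two arms, and the general text speaks of conclusions about treatment. Arm may well be the implied predictor. That stands as a statement about intent. It does not repair the text: the general passage concerns baseline confounding, and the authors wrote the arms out when specifying Hypothesis 2.

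The plan also promises a Bayesian supplement on the probability of effects of various sizes, which shows interest in more than significance. But that line sits in the power paragraph, which focuses on Aim 2, and it supplies no arm term for safety.

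It is fair to add that a pilot of 20 cannot establish safety even after the change. That stands, and it is why the fix asks for estimates with intervals.

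A reader might infer that the stated model becomes less likely to be significant as harm grows. This appears only if AEs do not rise at all in the harmed arm. With an AE shift one quarter of the symptom shift, the rates at harm 0/0.5/1/1.5 SD are about 25/26/29/34% at correlation 0.3 and flat near 64% at 0.5. The documents give no AE–symptom correlation and no reason to assume that AEs are unaffected. A reader might also infer that no comparison by arm will be made, or that rating levels will not be reported. The plan does not say that either; it leaves both unstated.

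**Conclusion.** The point holds as a statement about the written plan, not about what the authors meant. The only analysis stated for 1.c contains no treatment contrast, so neither a significant nor a null result from it answers the hypothesis. This follows from the wording and does not depend on the simulation.

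The percentages (about 5%, 25% and 64% with no effect, against 5% to 89% for an arm contrast across 0 to 1.5 SD) show only the size of the ambiguity under assumed correlations and normal scores. It should be corrected before analysis, and the remedy is small.

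The 1.b issue is secondary. The invariance argument is exact for a linear model, and the plan also allows other model families. The gap between the broad symptom wording in the aims and the two narrower outcomes in the analysis plan is a lesser specification matter. The main point does not rest on it.

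**What to change.** Replace the 1.c analysis sentence with a comparison of NRT + e-cigarette against NRT:

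- **BPRS negative symptoms:** the mixed model already planned, with arm, visit, arm-by-visit and the last value before product is supplied as baseline. Report the Week 5 arm difference with 95% CI.
- **MCCB:** Week 5 by arm, adjusted for Week 0, with 95% CI.
- **AEs and severe AEs:** tabulated by arm with exact 95% CIs.
- **Interpretation:** state in advance that a non-significant difference will not be reported as showing safety.

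For 1.b, report the level of each rating, or the proportion giving a favourable rating, with 95% CI in place of the model relating ratings to one another.

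Optionally, reconcile the symptom measures named for 1.c in the aims with those named in the analysis plan, and say which of the other scheduled scales belong to it.

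The cost is SAP wording and a few tables; the 1.c analyses use data already scheduled in Table 1. The downside is candour about precision. Week 5 intervals of ± 0.82 to 0.94 SD, or ± 1.02 SD with 7 completers per arm, and an upper limit of 31% after no events in 10, mean the results are estimates and the safety statement must be more cautious.
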